## 6.2.2 Responsibilities

Any quality issue noticed with the receipt or use of an IMP (deficiency in condition, appearance, pertaining documentation, labeling, expiration date, etc) must be promptly notified to the Sponsor. Some deficiencies may be recorded through a complaint procedure (see [Section 8.3.7](#)).

A potential defect in the quality of IMP may be subject to the initiation of a recall procedure by the Sponsor. In this case, the Investigator will be responsible for promptly addressing any request made by the Sponsor in order to recall the IMP and eliminate potential hazards.

Under no circumstances will the Investigator supply IMP to a third party (except for direct mail to participant shipment, for which a courier company has been approved by the Sponsor), allow the IMP to be used other than as directed by this clinical trial protocol, or dispose of the IMP in any other manner.

## 6.3 MEASURES TO MINIMIZE BIAS: RANDOMIZATION AND BLINDING

The randomized intervention kit number list is generated centrally by Sanofi, and IMPs are packaged in accordance with this list. The randomization and intervention allocation are performed centrally by IRT. The IRT generates the participant randomization list and allocates the intervention number and the corresponding intervention kits to the participants according to it. Before the study is initiated, the log-in information and directions for the IRT will be provided to each site.

Participants will be randomized in a 1:1 ratio treatment arm described in [Table 2](#).

Randomization will be stratified by screening blood eosinophil count ( $\geq 300$  cells/mm $^3$  or  $< 300$  cells/mm $^3$ ), background INCS use (yes or no) and region.

At Screening (Visit 1), the Investigator or designee will contact the IRT to receive the participant number. If a participant who had previously failed screening is approached for re-screening, a new ICF must be signed. In such case, a new participant number will be assigned by IRT.

A randomized participant is defined as a participant who has been allocated to a randomized intervention regardless of whether the treatment was administered or not (ie, participant registered by the IRT). A participant cannot be randomized more than once in the study.

Study intervention will be dispensed at the study visits summarized in the SoA ([Section 1.3](#)). Returned study intervention should not be re-dispensed to the participants.

## Methods of blinding

Dupilumab 300 mg and placebo 300 mg will be provided in identically matched 2 mL pre-filled syringes that are visually indistinguishable for each dose. Syringes and box will be labeled with a treatment kit number.

## Code breaking

The IRT will be programmed with blind-breaking instructions. In case of an emergency, the Investigator has the sole responsibility for determining if unblinding of a participant's intervention assignment is warranted. Participant safety must always be the first consideration in making such a determination. If the Investigator decides that unblinding is warranted, he/she may, at his/her discretion, contact the Sponsor to discuss the situation prior to unblinding a participant's intervention assignment unless this could delay emergency treatment of the participant. If a participant's intervention assignment is unblinded, the Sponsor must be notified within 24 hours after breaking the blind. The date and reason that the blind was broken must be recorded in the source documentation and eCRF, as applicable.

If the code is broken at the site level, the participant must withdraw permanently from IMP administration.

## 6.4 STUDY INTERVENTION COMPLIANCE

- The Investigator or his/her delegate must ensure that IMP is administered to each participant according to the labeling instructions.
- IMPs accountability:
  - Intervention units are returned by the participant at each visit. In case of direct mail to participant process, the intervention units can be returned by the carrier (if defined in the contract),
  - The Investigator or his/her delegate counts the number of remaining kits/pre-filled syringes and fills in the Intervention Log Form,
  - The Investigator or his/her delegate records the dosing information on the appropriate pages of the eCRF,
  - The monitor in charge of the study then checks the eCRF data by comparing them with the IMP that he/she has retrieved, and the intervention log forms.

When participants are dosed at the site, they will receive study intervention directly from the Investigator or designee, under medical supervision. The date and time of each dose administered in the clinic will be recorded in the source documents and recorded in the eCRF. The dose of study intervention and study participant identification will be confirmed at the time of dosing by a member of the study site staff other than the person administering the study intervention.

When participants self-administer study intervention(s) at home, compliance with study intervention will be assessed at each visit. Compliance will be assessed by checking participant home-dosing diary and used/unused kits/pre-filled syringes during the site visits and documented

in the source documents and eCRF. Changes(s) from the prescribed dosage regimen should be recorded in the eCRF.

Detailed instructions for transport, storage, preparation, and administration of IMP are provided to the participant. For doses not given at the study site, participants will complete a dosing diary to document compliance with self-injection (or caregiver) of IMP, location of injection, and any symptoms. The diary will be kept as source data in the participant's study file.

A record of the number of kits/pre-filled syringes dispensed to and taken by each participant must be maintained and reconciled with study intervention and compliance records. Relevant data from the dosing diary will be recorded in the eCRF.

## **6.5 CONCOMITANT THERAPY**

Any medication or vaccine (including over the counter or prescription medicines, vitamins, and/or herbal supplements or other specific categories of interest) that the participant is receiving at the time of enrollment or receives during the study must be recorded along with:

- Reason for use.
- Dates of administration including start and end dates.
- Dosage information including dose and frequency.

The Sponsor or Sponsor representative(s) should be contacted if there are any questions regarding concomitant or prior therapy.

### **6.5.1 Background treatments**

Participants should continue their permitted background INCS spray during the study, if they were on stable dose of INCS (except for Xhance™) for at least 4 weeks prior to screening. From the time of screening, they should not change their background medications.

### **Permitted concomitant medication**

The following treatments are allowed:

- Intranasal corticosteroid spray (except for Xhance™) is permitted as background medication that it should be on the stable dose for at least 4 weeks prior to study screening, and participants must maintain the same INCS throughout the study treatment period if initiated before enrollment.
- Single dose of topical decongestants administration, for example, oxymetazoline hydrochloride (to reduce the swelling and widen the path for the endoscope) as well as a topical anesthetic (eg, lidocaine) are allowed before nasal brushing or before endoscopy.
- Administration of short courses antibiotics for a concurrent infection or CRSsNP worsening /acute sinusitis, is allowed during the study (reason for and duration of treatment should be documented in the eCRF) (see [Section 6.5.3](#)).

- Short-acting  $\beta$ 2-adrenergic receptor agonists (SABA), long-acting  $\beta$ 2-adrenergic receptor agonists (LABA), and long-acting muscarinic acetylcholine receptor antagonists (LAMA).
- Methylxanthines (eg, theophylline, aminophylline).
- Inhaled corticosteroids.
- Systemic antihistamines.
- Leukotriene antagonists/modifiers are only permitted during the study, for participants who have been on a continuous treatment for  $\geq$ 30 days prior to Visit 1.
- Allergen immunotherapy in place for  $\geq$ 3 months and dose stable for 1 month prior to Visit 1 is permitted.
- Short courses of SCS to treat other serious co-existing diseases (such as asthma exacerbation) or for AEs are allowed (see [Section 6.5.3](#)).

Other concomitant medication may be considered on a case-by-case basis by the Investigator in consultation with the Sponsor or Sponsor representative(s) if required.

### **6.5.2 Prohibited medications**

The following concomitant treatments are not permitted during the screening period and the randomized treatment period:

- Any systemic immunosuppressive treatment, such as methotrexate, cyclosporine, mycophenolate, tacrolimus, etc.
- Initiation of allergen immunotherapy.
- Intranasal corticosteroid drops; intranasal steroid emitting devices/stents; nasal spray using Exhalation Delivery System such as XhanceTM.
- All forms of SCS are prohibited during screening and study treatment period except for short-term courses ( $\leq$ 2 weeks) of OCS can be used as rescue during treatment period (see [Section 6.5.3](#)).
- Live attenuated vaccines.
- Intravenous immunoglobulin (IVIG) therapy.
- Other monoclonal antibodies (biological immunomodulators), including but not limited to anti-IgE, anti-IL-5, and anti-tumor necrosis factor (TNF), etc.
- Systemic antibiotics are prohibited during screening and study treatment period except for rescue use (see [Section 6.5.3](#)).

### **6.5.3 Rescue medicine**

During the study treatment and follow-up periods, based on clinical evaluation, in case of worsening of signs and/or symptoms/acute sinusitis requiring medical intervention, the Investigator may consider rescue treatment with:

- Systemic antibiotics (up to 2 weeks) in case of acute infection.
- Short course OCS (prednisone or equivalent prednisolone up to 14 days; avoid use 4 weeks before Week 24 or Week 52, where applicable).
- Sinonasal surgery for CRSsNP (8 weeks of IMP treatment is recommended prior to surgery to allow onset of treatment effect).
- Intranasal corticosteroids spray (initiation of INCS spray or change in dosing of a background INCS during the study period).

Participants receiving rescue treatment other than surgery during the study should continue on study drug unless the Investigator decides to withdraw the study treatment. Before starting treatment with OCS participants should come to the study site for the clinical assessments. It is recommended to avoid use of OCS as rescue therapy during the Week 20 to Week 24 or the Week 48 to Week 52. If a participant must use OCS during this period to control worsening of symptoms based on Investigator judgment the site should make every efforts to schedule the Week 24 CT scan or the Week 52 CT scan prior to OCS rescue therapy.

For participants who undergo or are planned for surgery for CRSsNP the Investigator may decide to continue IMP up to the time of surgery or end of treatment (EOT) whichever date comes first. At the time of surgery participants will be permanently discontinued from study treatment and assessed as soon as possible using the procedures normally planned for the EOT Visit. In any case participants who prematurely discontinued the treatment will be encouraged to return to the study site for the efficacy and safety assessments planned at EOT Visit and for additional visits.

Additional appropriate medical/therapy per local guideline or per Investigators decision may be considered to use as rescue medicine. The date and time of rescue medication administration as well as the name and dosage regimen of the rescue medication must be recorded in the eCRF.

## **6.6 DOSE MODIFICATION**

No IMP dose modification is allowed.

## **6.7 INTERVENTION AFTER THE END OF THE STUDY**

Sponsor will not be responsible for intervention after the EOS Visit. Study intervention after the EOS Visit will be at the discretion of Investigator or treating physician.

## 7 DISCONTINUATION OF STUDY INTERVENTION AND PARTICIPANT DISCONTINUATION/WITHDRAWAL

### 7.1 DISCONTINUATION OF STUDY INTERVENTION

#### 7.1.1 Definitive discontinuation

In rare instances, it may be necessary for a participant to permanently discontinue study intervention. If study intervention is permanently discontinued, the participant will remain in the study to be evaluated for safety and efficacy. See the SoA ([Section 1.3](#)) for data to be collected at the time of discontinuation of study intervention and follow-up and for any further evaluations that need to be completed.

The participants may withdraw from treatment with the IMP if he or she decides to do so at any time for any reason, or based on the Investigator's decision. All efforts should be made to document the reason(s) for study intervention discontinuation and recorded in the eCRF.

Participants must be permanently withdrawn from the study intervention for the following reasons:

- At their own request or at the request of their legally authorized representative (legally authorized representative means an individual or judicial or other body authorized under applicable law to consent on behalf of a prospective participant to participate in the procedure(s) involved in the research).
- If, in the Investigator's opinion, continuation in the study would be detrimental to the participant's well-being.
- At the specific request of the Sponsor.
- If the participant is treated with the specific prohibited medications mentioned in [Section 6.5](#).
- If the participant misses 2 consecutive IMP doses.
- In the event of a protocol deviation, at the discretion of the Investigator or the Sponsor.
- Any code broken at the requested of the Investigator.
- Pregnancy.
- Anaphylactic reactions or systemic allergic reactions that are related to IMP and require treatment (see [Section 10.9](#)).
- Diagnosis of a malignancy during the study, excluding carcinoma in situ of the cervix, or squamous or basal cell carcinoma of the skin.
- Any opportunistic infection or other infections whose nature or course may suggest an immunocompromised status (see [Section 10.10](#)).
- Serum alanine aminotransferase (ALT)  $>3 \times$  upper limit of normal (ULN) and total bilirubin  $>2 \times$  ULN (see [Section 10.6](#)).

- Serum ALT  $>5 \times$  ULN if baseline ALT  $\leq 2 \times$  ULN, or ALT  $>8 \times$  ULN if baseline ALT  $>2 \times$  ULN (see [Section 10.6](#)).

If a clinically significant finding is identified (including, but not limited to changes from baseline in QT interval corrected using Fridericia's formula [QTcF] after enrollment), the Investigator or qualified designee will determine if the participant can continue in the study and if any change in participant management is needed. This review of the electrocardiogram (ECG) printed at the time of collection must be documented. Any new clinically relevant finding should be reported as an AE.

Any abnormal laboratory value or ECG parameter will be immediately rechecked for confirmation within a reasonable timeframe as assessed by the Investigator before making a decision of definitive discontinuation of the IMP for the concerned participant.

### **Handling of participants after definitive intervention discontinuation**

If participants no longer wish to take the IMP, they will be encouraged to remain in the study.

The Investigators should discuss with them key visits to attend. The value of all their study data collected during their continued involvement will be emphasized as important to the public health value of the study.

Participants who withdraw from the study intervention should be explicitly asked about the contribution of possible AEs to their decision, and any AE information elicited must be documented.

Participants will be followed-up according to the study procedures specified in this protocol up to the scheduled date of study completion, or up to recovery or stabilization of any AE to be followed-up as specified in this protocol, whichever comes last.

Participants who discontinue the study intervention prematurely (prior to completing the treatment period) will perform, as soon as possible, the Early Termination Visit with all the assessments normally planned for the EOT Visit (refer to [Section 8.1.1](#)), to assure a complete clinical assessment in close temporal proximity to the premature termination of study intervention is available. A CT scan can be done at time of Early Termination Visit if the previous CT scan is performed at least 4 months ago. Otherwise, the CT scan should be performed at the next scheduled timepoint (ie, Week 24).

In addition, and to allow assessment of participant outcomes over the stipulated study period, participants will be asked and encouraged to complete all remaining study treatment visits and participate in all assessments according to the visit schedule with a  $\pm 3$  days window. Under exceptional circumstances when a participant cannot come to the site for a scheduled visit, a phone contact can be made. During the phone contact, at least information about AEs, concomitant medication, and the status of CRSsNP should be collected.

All cases of definitive intervention discontinuation must be recorded by the Investigator in the appropriate pages of the eCRF when considered as confirmed.

### **7.1.2 Temporary discontinuation**

Temporary intervention discontinuation may be considered by the Investigator because of suspected AEs. For all temporary intervention discontinuations, duration should be recorded by the Investigator in the appropriate pages of the eCRF.

Temporary intervention discontinuation decided by the Investigator corresponds to at least 1 dose not administered to the participant. Following a temporary interruption or missed dose, the study intervention should be reinitiated at the next scheduled administration, maintaining the planned dose.

If 2 consecutive IMP doses have been missed, the study intervention will be definitively discontinued (see [Section 7.1.1](#)). Investigator must contact the participant to instruct not to take any subsequent injection.

#### **7.1.2.1 Rechallenge**

Reinitiation of intervention with the IMP will be done under close and appropriate clinical/and or laboratory monitoring once the Investigator considers this to be appropriate according to his/her best medical judgment that the responsibility of the IMP(s) in the occurrence of the concerned event was unlikely and if the selection criteria for the study are still met (refer to [Section 5](#)).

## **7.2 PARTICIPANT DISCONTINUATION/WITHDRAWAL FROM THE STUDY**

- A participant may withdraw from the study at any time at his/her own request or if his/her caregiver(s) or may be withdrawn at any time at the discretion of the Investigator for safety, behavioral, compliance, or administrative reasons. This is expected to be uncommon.
- At the time of discontinuing from the study, if possible, an early follow-up/EOS Visit should be conducted, as shown in the SoA ([Section 1.3](#)).
- The participant will be permanently discontinued both from the study intervention and from the study at that time.
- If the participant withdraws consent for the disclosure of future information, the Sponsor may retain and continue to use any data collected before such a withdrawal of consent.
- If a participant withdraws from the study, he/she may request destruction of any samples taken and not tested; and the Investigator must document this in the site study records.
- All study withdrawals should be recorded by the Investigator in the appropriate screens of the eCRF and in the participant's medical records. In the medical record, at least the date of the withdrawal and the reason should be documented.
- In addition, a participant may withdraw his/her consent to stop participating in the study. A participant's decision to discontinue intervention should be distinguished from withdrawal of consent for follow-up visits and from withdrawal of consent for non-participant contact follow-up, eg, medical record checks. The site should document any case of withdrawal of consent.

Participants who have withdrawn from the study cannot be rerandomized (treated) in the study. Their inclusion and intervention numbers must not be reused.

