- c Participants who discontinue the study treatment prematurely (prior to completing Week 24 of treatment period) will perform the end of treatment (EOT) assessments at the time of discontinuation to assure a complete clinical assessment in close temporal proximity to the premature termination of study treatment. In addition, to allow assessment of participant outcomes over the stipulated study period, participants will be asked and encouraged to complete all remaining study visits and participate in all assessments according to the visit schedule.
- d Consent to be obtained for optional procedures (whole blood DNA, whole blood RNA sampling, and serum/plasma sampling for archival; human immunodeficiency virus (HIV) test if specific consent locally required).
- e Past medical history including allergic comorbidities (asthma, aspirin sensitivity, allergic rhinitis etc). Surgeries will be assessed including type and dates of sinonasal surgeries in the past. Systemic corticosteroids (SCS) use (number of courses, doses, way of administration and duration) in the past 2 years before V1 and/or contraindication/intolerance to SCS, as well as long-term antibiotics use (>2 weeks) in the previous year will be entered in the electronic case report form (eCRF).
- f Details on actual or planned date for surgery type and outcome (whenever possible) of surgery will be recorded in a specific eCRF page. If surgery is performed during the study treatment period or follow-up an adverse event (AE) or serious adverse event (SAE) page will be completed. Participants will be discontinued from study treatment and assessed as soon as possible using the procedures normally planned for the EOT Visit. If surgery is scheduled after the planned end of study, a follow-up contact(s) may be required to document the surgery date and outcome.
- g Nasal endoscopy: Endoscopy (including use of decongestants before the procedure) will be performed at Screening Visit only for eligibility confirmation. At V2, Investigator will review V1 results from central reader to confirm entry criteria and reconfirm eligibility based on review of inclusion/exclusion criteria.

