## 8.1 EFFICACY ASSESSMENTS

### 8.1.1 Computerized Tomography Scans using Lund-Mackay

Computerized tomography scans using the LMK allows the assessment of sinus opacification ([37](#)).

The CT scan LMK staging system represents the most widely established method of sinus CT scoring in clinical trials. The LMK total score is based on assessment of the CT scan findings for each sinus area (maxillary, anterior ethmoid, posterior ethmoid, sphenoid, and frontal sinus on each side). The extent of mucosal opacification is rated on a 3-point scale ranging from 0 = normal to 2 = total opacification. In addition, the ostiomeatal complex is graded as 0 = not occluded or 2 = occluded. The maximum score is therefore 12 per side for a maximum total score of 24, corresponding to the sum of all sinuses and the ostiomeatal unit.

This scoring system has been validated in several studies ([37, 38, 39](#)).

The CT scans should be performed anytime during the screening period before first administration of IMP at Visit 2 (baseline CT data), Visit 5 (Week 24). The Visit 7 (Week 52) CT scan is optional due to variable treatment period. Whenever possible a cone beam CT scan should be utilized. In countries for which a specific approval procedure for the CT scan is required by a different committee than the local IEC/IRB, a 4-month window is required between 2 CT scans. If a participant needs to be rescreened or is terminated early from the study intervention, the repeated CT scan or following CT scan must be done over a 4-month restriction window. If Participant who discontinue the study intervention prematurely, the CT scan will be performed as soon as possible, with all other assessments normally planned in EOT Visit as long as between 2 CT scans can meet a 4-month restriction window. Otherwise, the CT scan can be done in next scheduled visit.

It is recommended to avoid use of OCS as rescue therapy during the Week 20 to Week 24 or-the Week 48 to Week 52. If a participant must use OCS during this period to control CRSsNP worsening/acute sinusitis based on Investigator judgment the site should make every efforts to schedule the Week 24 CT scan or the Week 52 CT scan-prior to OCS rescue therapy.

The CT scan will be performed locally and reviewed centrally in a pre-specified manner as described in the Image Acquisition Standards (IAS) and Image Interpretation Standards (IIS) (refer [Section 1.3](#)).

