**Table 10 - Time window for efficacy variables**

Analysis visit	Target day	Time windows for							
		LMK /3-D CT	UPSiT, VAS	SNOT-22	Spirometry	ACQ-6	EQ-5D-5L	PGIS, HCRU/P	PGIC
Screening	-28 to -14				<14				
Baseline	1	<1-	<1-	<1-	-14-1-	1-	1-	<1-	
Week 2	15		1*-91						
Week 12	85				1*-126	1*-126		1*-126	1*-126
Week 24	169	1*-266	92-224	1*-224	127-266	127-224	1*-224	127-224	127-224
Week 40	281		225-322	225-322		225-322	225-322	225-322	225-322
Week 52	365	267-d	323-d	323-d	267-d	323-d	323-d	323-d	323-d
EOS*	NA		NA	NA	NA	NA			

d: planned EOT date, EOT: End of Treatment, EOS: End of Study

1-: up to randomization and before 1st dose date/time; 1\*: after randomization or 1st dose date/time

\* Data collected at the EOS visit will not be remapped

For the pharmacokinetics/pharmacodynamics variables summary, the reference date for the derivation of relative days of measurements will be the date of first IMP administration if the participant is treated with study intervention, or the randomization date if the participant is not treated. Pharmacokinetics /pharmacodynamics variables will be summarized by the analysis window defined in **Table 11** for the by visit descriptive analyses. All available values of measurements will be assigned to the appropriate visit window. In the event of multiple measurements of the same test in the same window, the one closest to the targeted visit date will be used for the by-visit summary. If they are at the same number of days away from the target day, the latest one will be used. For procedures planned on Visit 2, if it is done on the same date as the first IMP injection but the performance time is missing, it will belong to the Visit 2 window.

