**Table 11 - Time window for pharmacokinetics/pharmacodynamics variables**

Analysis visit	Target day	Time windows for				
		Serum dupilumab, ADA	Blood biomarkers	Urine biomarkers	Nasal secretions for protein biomarkers	Nasal brushing for RNA and cytology
Screening	-28 to -14					
Baseline	1	<1-	<1-	<1-	<1-	<1-
Week 2	15					
Week 12	85	1 + -126	1 + -126	1 + -126	1 + -126	
Week 24	169	127-266	127-266	127-266	127-266	1 + -266
Week 40	281					
Week 52	365	>266	>266	>266	>266	>266
EOS*	NA	NA				

1: up to randomization and before 1st dose date/time; 1+: after randomization or 1st dose date/time

\*PK and ADA data collected at the EOS visit will not be remapped

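### The protocol does not say which last visit applies to a participant who leaves the study before Week 24, and the SAP keeps efficacy values from an early EOS visit out of the Week 24 windows

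*Protocol*

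**What the plan says.** **Leaving the study.** Protocol 7.2: "At the time of discontinuing from the study, if possible, an early follow-up/EOS Visit should be conducted, as shown in the SoA". The same section adds: "The participant will be permanently discontinued both from the study intervention and from the study at that time".

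**Stopping drug early.** Under Protocol 7.1.1 (handling after definitive discontinuation), these participants "will perform, as soon as possible, the Early Termination Visit with all the assessments normally planned for the EOT Visit". SoA footnote c repeats this for stops before Week 24: they "will perform the end of treatment (EOT) assessments at the time of discontinuation". The CT is conditional: "A CT scan can be done at time of Early Termination Visit if the previous CT scan is performed at least 4 months ago". Otherwise it waits for the next scheduled time point, Week 24.

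**What each visit collects (SoA, Protocol 1.3).** SNOT-22, UPSIT, VAS, spirometry and ACQ-6 are marked at both EOT (Visit 7) and EOS (Visit 8), the last two after screening only in participants with asthma. CT, EQ-5D-5L, PGIS, PGIC and laboratory tests are marked at EOT but not at EOS. Protocol 8.1.1 likewise lists CT only at screening, Week 24 and, optionally, Week 52.

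**How the SAP assigns values.** SAP 5.4 assigns scheduled efficacy measurements to Table 10 windows by study day and takes the value closest to the target day. Unscheduled efficacy values enter the by-visit summaries if re-allocated to a scheduled visit. For EOS the Table 10 footnote reads: "Data collected at the EOS visit will not be remapped". It makes no exception for an early EOS visit. SAP 3.2.2, 3.3.2 and 3.4.2 impute no missing data beyond WOCF after surgery or systemic corticosteroids.

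**The concern.** A participant who leaves the study while on drug meets both conditions on the same day, so two last-visit rules apply and no passage ranks or combines them. A site that reads only 7.2 holds the EOS visit and takes no CT.

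Section 7.1.1 does not cover every case even when it is followed. Take a participant who stops drug early, has the Early Termination Visit, has the CT deferred to Week 24 because the 4-month limit has not passed, and then leaves the study after that limit but before Week 24. The only visit left is the early EOS visit, which has no CT.

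The SAP then makes inclusion depend on the visit label. A value observed on Day 160 counts towards Week 24 if recorded at an EOT visit, and does not if recorded at an early EOS visit. It stays under EOS, beside values taken about 12 weeks after the end of treatment, so that summary mixes two treatment states. Leaving the study is plausibly related to outcome, and with about 15 participants per arm in the primary population one or two people matter.

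**Working it through.** **1. The plan's own figure.** SAP section 4 gives SD 5, 15 per arm with eosinophils at or above 300 cells/mm³ and 10% dropout, for a half-width of approximately less than 3. With n = 15 × 0.9 = 13.5 and half-width = t(0.975, n−1) × 5/√n:

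| n | half-width |
|---|---|
| 13 | 3.02 |
| 13.5 | 2.95 |
| 14 | 2.89 |
| 15 | 2.77 |

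The normal quantile at n = 13.5 gives 1.96 × 5/√13.5 = 2.67. The planning figure is reproduced and is not in dispute.

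**2. When an early CT is permitted.** The documents do not give 4 months in days; I assume 112 to 122. The baseline CT is taken between Day −31 and Day −1. Earliest permitted day = CT day + interval + 1 (no Day 0):

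- earliest: −31 + 112 + 1 = Day 82
- latest: −1 + 122 + 1 = Day 122

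Before that day neither section gives a CT. The gap matters for LMK only from that day to Day 169 (Week 24). If departures are uniform over the 168 days, the share is (169 − 122)/168 = 28% to (169 − 82)/168 = 52%.

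**3. Size for LMK.** Dropout of 10% is 1.5 of 15. At most 0.28 × 1.5 = 0.4 to 0.52 × 1.5 = 0.8 participant has an obtainable CT that an EOS-only visit would miss, or roughly half a participant. Adding 0.5 to 13.5 gives n = 14 and moves the half-width from 2.95 to 2.89. Over the whole range (n = 13.92 to 14.28) it becomes 2.90 to 2.85. Table 10 places an LMK value up to Day 266 in Week 24, so a CT at an early visit would count. The secondary LMK comparison uses the same CT in both arms.

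**4. Size for visit-based exploratory endpoints.** Share of pre-Week 24 departures on a day inside the Table 10 Week 24 window, same uniform assumption:

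| Endpoint | Week 24 window (days) | Share up to Day 169 | Of 1.5 leavers |
|---|---|---|---|
| SNOT-22 | after randomization to 224 | nearly all | up to 1.5 |
| UPSIT, VAS | 92–224 | (169 − 92)/168 = 46% | 0.7 |
| ACQ-6 | 127–224 | (169 − 127)/168 = 25% | 0.4 |
| Spirometry | 127–266 | 25% | 0.4 |

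The last two rows are before restriction to participants with asthma.

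**5. One case on both labels.** A SNOT-22 on Day 160 at an EOT visit maps to Week 24. From a re-allocated unscheduled visit it can also map there. At an early EOS visit it does not. An on-drug leaver with only the EOS visit has no other post-baseline SNOT-22, since the first scheduled one is at Week 24, so Week 24 is missing. A leaver who had an Early Termination Visit on, say, Day 60 keeps that SNOT-22 as the Week 24 value and loses the later one nearer Day 169. That person's Day 60 UPSIT and VAS fall in the Week 2 window (up to Day 91), so those are missing at Week 24.

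**The case against.** The strongest reply is that the protocol already asks for the EOT assessments. An on-drug leaver is also a premature treatment discontinuer, 7.1.1 and footnote c make no exception for that person, and nothing says the EOS visit replaces the EOT visit. This stands for the on-drug leaver: the defect is an unresolved overlap, not an instruction to omit EOT. It does not answer the case of earlier drug stop, deferred CT and later departure, because the Early Termination Visit has already been used.

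The no-remap rule also has a sound purpose. After 24 weeks of treatment the scheduled EOS visit falls at Week 36 (Day 253), inside the spirometry Week 24 window, and should not count as Week 24. That justifies the rule for the scheduled EOS visit, not for an early one. Remapping has a cost too: the SNOT-22 window opens just after randomization, so very early values could count as Week 24. Early EOT values already do.

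A reader might infer more than the documents support:

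- *Outcomes are lost only for study leavers.* No. A treatment discontinuer inside the 4-month limit also gets no CT at EOT, and has no LMK value if Week 24 is then missed.
- *The EOT visit always includes a CT.* It does so only when the 4-month limit allows.
- *The SAP never maps, or discards, EOS data.* EOS is its own analysis visit and is summarized. Diary data, including sTSS, are windowed by day in Table 8, and Table 9 has no EOS exception for safety data. Participants with surgery or corticosteroid use still receive a WOCF value.
- *The footnote affects the primary endpoint.* No LMK is scheduled at EOS, so there is nothing to remap. The LMK loss comes only from the absent CT.
- *PK and ADA are lost as well.* The SAP plans both at EOS (3.7.1.1, 3.7.1.2), and the Table 11 footnote provides for them.

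**Conclusion.** The point holds as a gap between sections. The protocol leaves open whether a participant leaving before Week 24 has EOT, EOS or both. If only the early EOS visit is held, a permitted CT is not taken, and observed SNOT-22, UPSIT, VAS, ACQ-6 and spirometry values are excluded from Week 24 by visit label.

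The size is small: about half a participant of 15 for LMK, taking the half-width from about 2.95 to 2.89, and otherwise exploratory endpoints in a study that tests no hypotheses. The figures assume uniform departures before Week 24, 4 months equal to 112 to 122 days, and that every dropout leaves the study and attends a last visit. That last assumption makes them upper bounds: 7.2 expects withdrawal to be uncommon, and a participant lost to follow-up attends no visit. The documents give no basis for estimating any bias. This is a cheap improvement, not a threat to the primary result.

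**What to change.** **Protocol 7.2.** Reconcile it with 7.1.1 and footnote c by adding one sentence: a participant who leaves the study before the planned EOT date has, if possible, the EOT-column assessments, with CT only under the existing 4-month limit. State that this also applies to a participant who stopped drug earlier and whose CT was deferred.

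**SAP Table 10 footnote.** Limit it to the scheduled post-treatment EOS visit. Efficacy values from an early EOS visit before the planned EOT date are assigned to the Table 10 windows under the existing closest-to-target rule.

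**Cost.** Two sentences, settled before database lock. No new type of procedure is added, although a participant who already had an Early Termination Visit would repeat that set once. Some early values would enter wide Week 24 windows, SNOT-22 above all, as early EOT values already do. Reporting how many Week 24 values come from early visits would make this visible.
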